#### Design Diagram – AMPLIFY TRIAL REPLICATION

## 5. Cohort Identification

### 5.1 Cohort Summary

This study will involve a new user, parallel group, propensity score-matched, retrospective cohort study design comparing apixaban to warfarin users. The patients will be required to have continuous enrollment during a baseline period of 180 days before initiation of apixaban or warfarin (index date). We will restrict the analyses to patients with a diagnosis of proximal DVT, PE, or both.

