### 5.2 Important steps for cohort formation

New use of apixaban, exposure, and warfarin, comparator, is defined as no use of either therapy in the 180 days prior to index date.

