#### 6.3.2 Study follow-up

Both as-treated (AT) and intention-to-treat (ITT) analyses will be conducted with treatment defined as the index drug on the day of cohort entry. Because adherence in the real-world databases is expected to be much worse than in the trial, the AT analysis is the **primary** analysis, as it targets the relative hazard of outcomes on treatment.

For the AT analyses, the follow-up will start the day after initiation of apixaban and comparator and will continue until the earliest date of the following events:

- The first occurrence of the outcome of interest, unless otherwise specified for selected outcomes,
- The date of end of continuous registration in the database,
- End of the study period,
- Measured death event occurs,
- Nursing home admission

- Nursing home admissions are considered a censoring event because the data sources utilized typically provide little to no data on a patient, particularly on drug utilization, after admission. We will utilize this as an exclusion reason for cohorts for the same reason.
- The date of drug discontinuation, defined as the date of the last continuous treatment episode of the index drug (apixaban and comparator) plus a defined grace period (i.e., 10 days after the end of the last prescription's days' supply in main analyses).
- The date of augmentation or switching from exposure to comparator or vice versa or augmentation/switching to any other NOAC (e.g. switching from apixaban to rivaroxaban would be a censoring event);
  - A dosage change on the index treatment does not fulfill this criterion
  - An added treatment that is not part of the exposure or comparator group does not fulfill this criterion
- Treatment of current episode of VTE with thrombectomy, insertion of caval filter, or use of fibrinolytic agent (streptokinase, alteplase, reteplase, tenecteplase)

For the intention-to-treat (ITT) analyses, the censoring based on the augmentation/switching and treatment discontinuation will be replaced with a maximum allowed follow-up time of 365 days.

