| • Acute symptomatic PE with evidence of thrombosis demonstrated by imaging as follows:
- an intraluminal filling defect in segmental or more proximal branches on spiral computed tomography (CT) scan; or
- an intraluminal filling defect or a sudden cutoff of vessels more than 2.5 mm in diameter on the pulmonary angiogram; or
- a perfusion defect of at least 75% of a segment with a local normal ventilation result (high probability) on ventilation/perfusion lung scan (VPLS) | Measured 180 days prior to and including day of drug initiation in any diagnosis position and in an inpatient or ED care setting

Pulmonary embolism (PE):
ICD-9 Dx: 415.xx
ICD-10 Dx: I26.xx                                            |                                                                                                                                                                                                                                                                                  |                                                                                                                                                                                                                                                                                                                                                                                                                                                                                                                    |

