# Appendix A

|                                                                                                                                                                                                     |                                                                                                                                                                                                                                                                                                                                                                                                                       |                                                                                                                                                                                       |  |
|-----------------------------------------------------------------------------------------------------------------------------------------------------------------------------------------------------|-----------------------------------------------------------------------------------------------------------------------------------------------------------------------------------------------------------------------------------------------------------------------------------------------------------------------------------------------------------------------------------------------------------------------|---------------------------------------------------------------------------------------------------------------------------------------------------------------------------------------|--|
| 
Thrombectomy, insertion of a caval filter, or use of a fibrinolytic agent to treat the current episode of venous thromboembolism (VTE).
                                                      | 
Measured 30 days prior and including the day of drug initiation in any diagnosis position in an inpatient or ED care setting
 
Thrombectomy:
CPT codes: 37184, 37185, 37186, 37187, 37188
HCPCS codes: C1757
 
Caval filter:
CPT codes: 37191, 37192, 37193
HCPCS codes: C1880
 
Fibrinolytic agent:
streptokinase, alteplase, reteplase, tenecteplase
 | 
Components will act as both exclusion criterion and censoring events
                                                                                                           |  |

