# Appendix B

|                                                                                            |               |               |         |               |               |         |               |               |           |               |               |         |
|--------------------------------------------------------------------------------------------|---------------|---------------|---------|---------------|---------------|---------|---------------|---------------|-----------|---------------|---------------|---------|
| Non-Frailty; n (%)                                                                         | 607 (41.2%)   | 1,297 (46.6%) | -0.11   | 986 (40.0%)   | 1,622 (41.9%) | -0.04   | 219 (4.4%)    | 103 (3.0%)    | 0.07      | 1,812 (20.3%) | 3,022 (30.0%) | -0.22   |
| Frailty Score (mean): Empirical Version 365 days, v2                                       |               |               |         |               |               |         |               |               |           |               |               |         |
| ...mean (sd)                                                                               | 0.17 (0.06)   | 0.17 (0.06)   | 0.00    | 0.16 (0.05)   | 0.15 (0.05)   | 0.20    | 0.10 (0.08)   | 0.09 (0.07)   | 0.13      | 0.13 (0.07)   | 0.14 (0.06)   | -0.15   |
| Healthcare Utilization                                                              |               |               |         |               |               |         |               |               |           |               |               |         |
| Any hospitalization; n (%)                                                                 | 1,342 (91.2%) | 2,517 (90.4%) | 0.03    | 2,456 (99.7%) | 3,872 (99.9%) | -0.04   | 4,571 (91.7%) | 2,940 (86.3%) | 0.17      | 8,369 (93.8%) | 9,329 (92.7%) | 0.04    |
| Any hospitalization within prior 30 days; n (%)                                            | 1,218 (82.7%) | 2,064 (74.2%) | 0.21    | 2,325 (94.4%) | 3,266 (84.3%) | 0.33    | 3,605 (72.3%) | 2,224 (65.3%) | 0.15      | 7148 (80.1%)  | 7554 (75.1%)  | 0.12    |
| Any hospitalization during prior 31-180 days; n (%)                                        | 210 (14.3%)   | 596 (21.4%)   | -0.19   | 279 (11.3%)   | 830 (21.4%)   | -0.28   | 1,509 (30.3%) | 1,094 (32.1%) | -0.04     | 1998 (22.4%)  | 2520 (25.0%)  | -0.06   |

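### The exclusion for thrombectomy, caval filter or fibrinolysis of the current VTE searches 30 days, while the qualifying VTE may be 180 days old, so treatment of older qualifying events goes unseen

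*Combined protocol and SAP*

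**What the plan says.** - **Qualifying event.** In the Appendix A inclusion criteria, the DVT row and the PE row carry the same window: "Measured 180 days prior to and including day of drug initiation in any diagnosis position and in an inpatient or ED care setting". The event may lie anywhere from day -180 to day 0.
- **Exclusion.** The trial criterion in Appendix A covers thrombectomy, caval filter insertion or "use of a fibrinolytic agent to treat the current episode of venous thromboembolism (VTE"). It is tied to the episode and has no day limit. The plan's implementation is "Measured 30 days prior and including the day of drug initiation in any diagnosis position in an inpatient or ED care setting", that is, day -30 to day 0. No reason for 30 days is given.
- **Second use of the same components.** Appendix A adds: "Components will act as both exclusion criterion and censoring events". Section 6.3.2 lists the censoring event as "Treatment of current episode of VTE with thrombectomy, insertion of caval filter, or use of fibrinolytic agent", and as-treated follow-up starts the day after initiation.
- **Other rules that might keep the event recent.** Section 5.2 describes new use as "defined as no use of either therapy in the 180 days prior to index date". This restricts prior drug use, not the age of the VTE. The trial limits on heparin or vitamin K antagonist treatment before the first study dose are marked not applicable in Appendix A.
- **Data.** Section 5.1 requires 180 days of continuous enrollment before the index date, so claims for days -180 to -31 are available.

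**The concern.** The exclusion is meant to describe how the qualifying VTE was treated, but its window is shorter than the one in which that VTE may fall. The same procedure excludes a patient on day -20, censors on day +5 and is ignored on day -60.

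Elsewhere the plan follows the trial's time limits closely: 6 months becomes 180 days, 2 months becomes 60 and 1 week becomes 7. Here the trial's anchor is the episode, and 30 days is the plan's own figure.

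At stake is whether the cohort matches the population of the replicated trial. Patients whom the trial would have turned away can enter, provided they start the study drug more than 30 days after the procedure. Because Appendix B has no thrombectomy, filter or fibrinolysis variable, the propensity score does not adjust for these treatments directly.

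**Working it through.** **1. Windows side by side.** The qualifying VTE may fall on day -180 to day 0 (181 days). The procedure search covers day -30 to day 0 (31 days). The uncovered part is day -180 to day -31: 150 of 181 days (83%). A late procedure for an older VTE, done in the last 30 days, is still found. Only procedures on day -31 or earlier are missed.

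**2. Exclusion #6 in the flowchart (Section 5.3).** The subtractions are correct and give the removal rates:

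- Optum: 8,579 - 211 = 8,368; 211/8,579 = 2.46%
- MarketScan: 8,340 - 143 = 8,197; 143/8,340 = 1.71%
- Medicare: 20,771 - 24 = 20,747; 24/20,771 = 0.12%

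**3. Proxy for patients with an older event.** The VTE-to-index interval is not reported. The nearest available count comes from the PS-matched table in Appendix B (Healthcare Utilization): the row for any hospitalization minus the row "Any hospitalization within prior 30 days; n" (%). This assumes that the first row covers the 180-day baseline.

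| Database | Warfarin | Apixaban | Both arms |
|---|---|---|---|
| Optum | 438 - 374 = 64 | 453 - 364 = 89 | 153 |
| MarketScan | 1,379 - 1,287 = 92 | 1,380 - 1,302 = 78 | 170 |
| Medicare | 1,564 - 1,204 = 360 | 1,555 - 1,229 = 326 | 686 |
| Pooled | 516 (14.5% of 3,570) | 493 (13.8% of 3,570) | 1,009 (14.1% of 7,140) |

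**4. Scenario for extra exclusions.** Assumption: procedures are as frequent among these patients as in the flowchart step.

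- Each database's own rate: 153 × 2.46% + 170 × 1.71% + 686 × 0.12% = 3.8 + 2.9 + 0.8 = about 7.5 patients.
- One rate for all 1,009: Medicare's rate gives 1.2, MarketScan's 17.3 and Optum's 24.8, so about 1 to 25. The top of this range puts Optum's 2.46% on 686 Medicare patients whose own rate is 0.12%.

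**5. Effect on events and power.** The plan's pooled figure in Section 10 reproduces. Events = 7,140 × 13.74/1,000 = 98.1036. Power = Φ(|ln(0.84/1.8)| × √98.1036 / 2 - 1.96) = 0.9652.

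- Removing 7.5 patients costs 7.5 × 0.01374 = about 0.1 expected event; removing 25 costs about 0.3.
- With 25 removed: 97.76 events, power 0.9647.
- With all 1,009 removed, an extreme case: 84.24 events, power 0.938.

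**6. Quality of the proxy.** It can miss in both directions.

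- Matched patients hospitalized in days 31 to 180 number 851 + 833 = 1,684. Subtracting 1,009 leaves 675 admitted in both windows. They are not counted, although their qualifying VTE could be the earlier admission.
- Another 7,140 - 3,381 - 3,388 = 371 matched patients had no baseline hospitalization. They presumably qualified through an ED code of unknown date and are not counted either.
- In the other direction, an admission need not be for VTE, and a patient admitted earlier for something else may have a VTE code from an ED visit in the last 30 days.

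**The case against.** **The number is tiny.** About 7 to 8 of 7,140 patients is 0.1%, and power does not move. This stands, and it is why the point is minor.

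**A short look-back is a fair proxy for a current episode; the odd feature is that an acute VTE may be 180 days old.** There is force in this, and lengthening the procedure search leaves the patients with old events in the cohort. But the plan does not give this rationale, and while it accepts a 180-day-old event as the qualifying one, that event is the current episode for the exclusion. New users with no recent oral anticoagulant may seldom have an old VTE, but the interval is not reported.

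**Other rules may cover part of the gap.** The major-surgery exclusion looks back 60 days over a procedure code range from which codes were selected. The selection is not shown, so overlap for days -60 to -31 can be neither confirmed nor ruled out. Even full overlap would leave days -180 to -61 open.

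**A stronger reading: the exclusion acts unequally by arm and biases the comparison.** A reader might infer this from the unmatched table, where the proxy is 1,221/8,919 (13.7%) for warfarin and 1,775/10,063 (17.6%) for apixaban, and in MarketScan 131/2,464 (5.3%) and 606/3,874 (15.6%). The documents do not support it for the planned analysis, which is matched. There the pooled proxy is 14.5% and 13.8%, and the pooled standardized differences for hospitalization in the last 30 days and in days 31 to 180 are -0.02 and 0.01. Optum alone still differs (64/490 = 13.1% and 89/490 = 18.2%), but at Optum's rate the 25-patient gap is 25 × 2.46% = about 0.6 patient.

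**A second stronger reading: 14.1% is an upper bound, or MarketScan's 170 is an exact count.** Neither follows, for the reasons in step 6 of the working.

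**Conclusion.** The mismatch is real and stands in the current text. As written, Appendix A admits patients whose qualifying VTE was treated by thrombectomy, filter or fibrinolysis in days -180 to -31, although the replicated criterion excludes them. The censoring rule acts only after the index date and does not repair this.

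The size cannot be derived from the documents, which give neither the VTE-to-index interval nor procedure counts for days -180 to -31. On the hospitalization proxy, and assuming that flowchart rates carry over, about 7 to 8 matched patients are affected, with a scenario range of about 1 to 25. The proxy is not a bound. Nothing in the documents shows a bias between the matched arms, and pooled power remains about 96.5%. Severity is minor: a departure from the trial criterion that is cheap to correct, not a threat to the result.

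**What to change.** Run the thrombectomy, filter and fibrinolytic search from the date of the qualifying VTE code through the index date. State which date is the anchor when a patient has several VTE codes in the 180 days. Then re-run the flowchart and refit the propensity score before the comparative analyses, whose section (13) is still blank.

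Do not simply extend the search to a fixed day -180. That would also remove patients whose procedure or lysis came before the qualifying VTE, whom the trial criterion does not exclude.

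Report the VTE-to-index interval by arm and database, so that a reader can see how many patients the change concerns. If 30 days is intended, Appendix A should say why and reconcile it with the 180-day inclusion window.

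Cost: an anchor date in place of a fixed window, one re-run, and the probable loss of a few patients.

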| Excluded based on Inclusion # 3b - Acute Symptomatic PE and based on Inclusion # 4 - Age                                                                                                                                                                                                                                                      | -4,641   | 8,593   | -2852    | 8,382   | -21,229    | 20,793    |
| Excluded based on Exclusion # 1 - pregnancy                                                                                                                                                                                                                                                                                                   | -14      | 8,579   | -42      | 8,340   | -22        | 20,771    |
| Excluded based on Exclusion # 6 - Thrombectomy, Insertion of Caval Filter, or Use of Fibrinolytic Agent                                                                                                                                                                                                                                       | -211     | 8,368   | -143     | 8,197   | -24        | 20,747    |
| Excluded based on Exclusion # 7 - Active bleeding (HAS_BLED Score >=3), based on Exclusion # 10A - Mechanical Valve, and based on Exclusion # 11.1 - Intracranial Bleeding                                                                                                                                                                    | -3,708   | 4,660   | -1447    | 6,750   | -11,558    | 9,189     |
| Excluded based on Exclusion # 11.2 - Intraocular Bleeding                                                                                                                                                                                                                                                                                     | 0        | 4,660   | 0        | 6,750   | 0          | 9,189     |
| Excluded based on Exclusion # 11.3 - Gastrointestinal Bleeding                                                                                                                                                                                                                                                                                | -12      | 4,648   | -52      | 6,698   | -78        | 9,111     |

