| 
Subjects with an indication, other than VTE, intended for long-term treatment with a VKA such as:
                                                                                            | 
N/A
                                                                                                                                                                                                                                                                                                                                                                                                            |                                                                                                                                                                                       |  |
| 
Mechanical valve
                                                                                                                                                                             | 
Measured 180 days prior to and including the drug initiation in any diagnosis position and in an inpatient or outpatient care setting
 
Mechanical valve
ICD-9 Dx: V43.3x
ICD-10 Dx: Z95.2x, Z95.3x, Z95.4x
ICD-9 Px: 35.0x, 35.2x, 35.3x
ICD-10 Px: O2RGxxx, O2RFxxx, O2RHxxx, O2RJxxx, O2QGxxx, O2QFxxx, O2QHxxx, O2QJxxx
                                                        |                                                                                                                                                                                       |  |
| 
Atrial fibrillation or atrial flutter with moderate to high risk of systemic thromboembolism. Subjects with atrial fibrillation that appears to be associated with acute PE may participate.
 | 
N/A
                                                                                                                                                                                                                                                                                                                                                                                                            |                                                                                                                                                                                       |  |

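### The thrombectomy, caval filter and fibrinolytic definition, printed without ICD procedure codes, removes 0.12% of Medicare patients against 1.7–2.5% elsewhere and likely under-captures there

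*Combined protocol and SAP*

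**What the plan says.** The exclusion criteria table in Appendix A gives the operational definition. Its window and setting are "Measured 30 days prior and including the day of drug initiation in any diagnosis position in an inpatient or ED care setting". Thrombectomy is identified by "CPT codes: 37184, 37185, 37186, 37187, 37188" and HCPCS C1757. Caval filter is identified by "CPT codes: 37191, 37192, 37193" and HCPCS C1880. Fibrinolytic use is given as names only: "streptokinase, alteplase, reteplase, tenecteplase". No ICD-9 or ICD-10 procedure code is printed for any of the three.

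The table adds: "Components will act as both exclusion criterion and censoring events". Section 6.3.2 accordingly lists, among the events that end as-treated follow-up, "Treatment of current episode of VTE with thrombectomy, insertion of caval filter, or use of fibrinolytic agent".

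Other procedures in the same appendix do carry ICD procedure codes. Mechanical valve has "ICD-9 Px: 35.0x, 35.2x, 35.3x" together with ICD-10 procedure codes, and GI bleeding control and neurosurgery also have both.

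The opening notes of Appendix A say that full ICD-10 lists are kept in an external folder, and send the reader there for anything missing.

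**The concern.** The flowchart row "Excluded based on Exclusion # 6 - Thrombectomy, Insertion of Caval Filter, or Use of Fibrinolytic Agent" shows a very low yield in the database with the most patients at that step. A definition that searches hospital care for procedures, but lists no ICD procedure codes, may work at a different sensitivity in each data source.

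Two things are at stake. First, an exclusion taken from the trial would be applied unevenly, so the pooled cohort would not be defined in the same way across databases. Second, the primary as-treated analysis uses the same components to stop follow-up, so follow-up might also be defined unevenly. Medicare contributes 3,398 of the 7,140 matched patients and about 50 of the 98 expected events (Section 10), so it is not a minor stratum.

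**Working it through.** **Inputs (Section 5.3 flowchart).** At risk before this step: Optum 8,579; MarketScan 8,340; Medicare 20,771. Removed: 211; 143; 24.

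**1. The plan's own figures reproduce.** 8,579 − 211 = 8,368; 8,340 − 143 = 8,197; 20,771 − 24 = 20,747. All match the flowchart.

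**2. Proportion removed.**
- Optum: 211/8,579 = 2.46%
- MarketScan: 143/8,340 = 1.71%
- Medicare: 24/20,771 = 0.116%

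**3. Ratio to Medicare.** The 95% CI uses SE(log ratio) = √(1/x − 1/n + 1/24 − 1/20,771).
- Optum: 2.459/0.1155 = 21.3 (14.0–32.4)
- MarketScan: 1.715/0.1155 = 14.8 (9.6–22.8)

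Chance does not explain the gap. In raw counts the factors are smaller: 211/24 = 8.8 and 143/24 = 6.0.

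**4. Is Medicare low at other steps too?** Flowchart proportions for two later exclusions:

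| Step | Optum | MarketScan | Medicare |
|---|---|---|---|
| Head or major trauma | 60/4,648 = 1.29% | 65/6,698 = 0.97% | 96/9,111 = 1.05% |
| Active liver disease | 133/4,495 = 2.96% | 142/6,580 = 2.16% | 226/8,871 = 2.55% |

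Medicare is in line at both.

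**5. Does recent hospital care explain it?** Appendix B (unmatched table), any hospitalization in the prior 30 days, both arms together:
- Optum: (1,218 + 2,064)/4,255 = 77.1%
- MarketScan: (2,325 + 3,266)/6,338 = 88.2%
- Medicare: (3,605 + 2,224)/8,389 = 69.5%

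The ratios to Medicare are 1.11 and 1.27, far short of 15–21. These figures describe the final cohorts rather than patients at this step, so they are indirect.

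**6. Illustration of size.** Assume that true Medicare use lies between the MarketScan and Optum rates, and that uncaptured patients pass the later steps at the average Medicare rate, 8,400/20,747 = 0.405.
- Expected removals: 20,771 × 1.715% = 356, to 20,771 × 2.459% = 511, instead of 24.
- Uncaptured at this step: 356 − 24 = 332, to 511 − 24 = 487.
- Remaining in the final cohort: 332 × 0.405 = 134, to 487 × 0.405 = 197. That is 1.6–2.3% of 8,400.
- The same rate gap applied to the matched Medicare patients: 3,398 × (1.715% − 0.116%) = 54, to 3,398 × (2.459% − 0.116%) = 80.

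**7. Censoring.** The only count is in Section 9: 755 of 7,140 (10.57%), with 497 (13.92%) on warfarin and 258 (7.23%) on apixaban. That row merges these treatments with NOAC switching and nursing home admission, and the table is pooled. The Medicare censoring rate for these treatments cannot be recovered from it.

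**The case against.** The strongest objection concerns cause. The same printed list serves all three databases, so the absence of ICD procedure codes cannot alone explain why only Medicare is low. Something specific to Medicare must also operate, such as claim structure, assignment of care setting, capture of infused drugs, practice or case mix. The plan describes none of these. Medicare patients are older (mean about 63, against 51 in MarketScan and 56 in Optum) and fewer had a recent hospitalization, so a somewhat lower rate is expected. This stands as a limit on what can be claimed, although step 5 shows that recent hospitalization accounts for little of the gap.

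Second, the codes may exist in the external folder. For ICD-10 that is possible and cannot be checked here. The note on omitted codes does not mention ICD-9 procedure codes, and it describes ICD-10 codes as mapped from ICD-9, of which this criterion prints none. The general pointer to the folder still leaves the matter open.

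Third, the illustration may be off. The next flowchart step (HAS-BLED ≥3, mechanical valve, intracranial bleeding) removes 11,558 of 20,747 in Medicare, and nothing shows that patients with a filter or lysis pass it at the average rate. Even at face value, 134–197 is 0.7–1.0% of the 19,002 patients in the three final cohorts, and no difference by arm is shown.

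A reader might infer that the missing codes are proven to cause the gap, or that under-capture of censoring in Medicare has been demonstrated. The documents support neither.

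**Conclusion.** The definition as printed is incomplete by the plan's own practice, and its Medicare yield is out of line by a margin that neither chance nor recent hospitalization explains and that two later exclusions do not share. Likely under-capture of the exclusion in Medicare is the reasonable reading. Likely under-capture of as-treated censoring follows only from the shared definition.

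The size is modest: about 1.6–2.3% of the final Medicare cohort, on the assumptions that true use falls between the MarketScan and Optum rates and that later retention is average. The documents give no true Medicare rate, and the direction of any effect on the hazard ratio is unknown.

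Two further readings should be avoided. The 15–21-fold figure applies to proportions; it does not mean that many times fewer patients, since the counts differ 6- to 9-fold. Equal rates across databases are also not an established target, because true use may differ. This is a low-severity point, worth settling because the remedy is specific and cheap.

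**What to change.** - Confirm whether ICD procedure codes were applied for this criterion in each database.
- If they were not, add ICD-9 and ICD-10 procedure codes for the three treatments to both the exclusion and the censoring definitions, in all databases.
- Check how care setting and infused drugs are captured in Medicare, since added codes may not close the gap if the cause lies there.
- Re-run cohort assembly and matching before the comparative analysis. Section 13 records no date for that analysis, so this still appears possible.
- Report the exclusion components, and the censoring components now merged in Section 9, separately by database and arm. Explain any remaining Medicare gap rather than requiring equal rates.

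The cost is a code-list extension, a re-run, and a loss of about 2% of Medicare patients if the illustration is near the truth.
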